### **8.9.2.      Bone Marrow Aspirate and Biopsy for Disease Assessment**

Historical bone marrow aspirates and biopsies at screening will not be accepted; a bone marrow aspirate and biopsy must be performed for study entry to collect mandatory biomarker assessments. The bone marrow aspirate and/or biopsy should be performed after all other eligibility criteria have been met. Bone marrow aspirates and/or biopsies performed as standard of care throughout the study should also be captured on the appropriate eCRF.

A sufficient bone marrow aspirate and bone marrow core biopsy must be collected for all subjects at each of the disease assessments for local pathology assessment, mandatory biomarker assessments and retrospective central lab response analysis.

## **9. SAFETY MONITORING AND REPORTING**

### **9.1. Adverse Events (AEs)**

#### **9.1.1. Adverse Event Definition**

For the purposes of this protocol, an AE is defined as any untoward medical occurrence associated with the use of a drug in humans, whether considered drug related, that occurs after a subject provides informed consent and through the follow-up period. Both nonserious and serious AEs (SAEs) will be monitored throughout the study.

A pre-treatment event (PTE) is one that occurs after the time of informed consent (e.g., during the screening process) but prior to study drug administration. PTEs directly related to a study test or procedure should be reported during the Screening period.

Conditions that were already present at the time of informed consent should be recorded on the Medical History form in the eCRF.

Abnormal laboratory values or test results occurring after informed consent constitute AEs only if they induce clinical signs or symptoms, are considered clinically meaningful, require therapy (e.g., hematologic abnormality that requires transfusion), or require changes in the study drug(s).

Progression of the cancer under study is not considered an adverse event unless it results in hospitalization or death.

Hospitalization of a subject to allow for observation and management (e.g., IV hydration) for the purpose of TLS prophylaxis will not be captured as an SAE unless there is an additional reason for hospitalization or an additional criterion for seriousness other than hospitalization is met.

#### **9.1.2. Serious Adverse Event Definition**

An SAE is defined as an event that meets at least 1 of the following criteria:

- **Death of Subject**
  - An event that results in the death of a subject.
- **Life-Threatening**
  - An event that, in the investigator's opinion, would have resulted in immediate fatality if the medical intervention had not been taken. This does not include an event that would have been fatal if it had occurred in a more severe form.
- **Hospitalization or Prolongation of Hospitalization**
  - An event that results in an admission to the hospital for any length of time or prolongs the subject's hospital stay. This does not include an emergency room visit or admission to an outpatient facility.
- **Congenital Anomaly**
  - An anomaly detected at or after birth, or any anomaly that results in fetal loss.
- **Persistent or Significant Disability/Incapacity**

- An event that results in a condition that substantially interferes with the activities of daily living of a study subject. Disability is not intended to include experiences of relatively minor medical significance such as headache, nausea, vomiting, diarrhea, influenza, and accidental trauma (e.g., sprained ankle).
- **Important Medical Event Requiring Medical or Surgical Intervention to Prevent Serious Outcome**
  - An important medical event that may not be immediately life-threatening or result in death or hospitalization, but based on medical judgment, may jeopardize the subject and may require medical or surgical intervention to prevent any of the outcomes listed above (i.e., death of the subject, life-threatening, hospitalization, prolongation of hospitalization, congenital anomaly, or persistent or significant disability/incapacity). Additionally, any elective or spontaneous abortion or stillbirth is considered an important medical event. Examples of such events include allergic bronchospasm requiring intensive treatment in an emergency room or at home, blood dyscrasias or convulsions that do not result in inpatient hospitalization, or the development of drug dependency or drug abuse.

For serious adverse events with the outcome of death, the date and cause of death will be recorded on the appropriate case report form.

Progressive disease is not considered a serious adverse event, unless symptoms and clinical manifestations of disease progression meet any of the SAE criteria noted above.

### **9.1.3. Events of Clinical Interest (ECI)**

Since NC525 has never been used in clinical trials, selected non-serious and serious adverse events are listed below as Events of Clinical Interest (ECI) and must be reported to the Sponsor **within 24 hours of awareness** by the Investigator. Since NC525 is a humanized monoclonal antibody, infusion reactions may occur. Furthermore, treatment of advanced myeloid neoplasms may cause differentiation syndrome and tumor lysis syndrome. Therefore, ECI are listed as precautionary for safety of subjects participating in NC525 study.

For the time period beginning with initiation of study treatment, any ECI, or follow up to an ECI, that occurs to any subject must be reported within 24 hours to the Sponsor.

Events of clinical interest for this trial include:

- Infusion Reaction
- Tumor Lysis Syndrome
- Differentiation Syndrome
- An adverse event meeting definition of a DLT as defined in [Section 5.9.1](#).

#### **9.1.4. Management of Myelosuppression Related to Disease**

Myelosuppression and the related adverse events (thrombocytopenia, anemia, neutropenia, and febrile neutropenia) are common in subjects with myeloid neoplasms. Subjects with baseline neutropenia might be particularly at high risk.

Anti-infective prophylaxis should be implemented per regional guidelines or institutional standards including appropriate prophylaxis for bacterial, viral, and fungal infections. Treatment of sepsis and other infections (e.g. viral, other infections) should be managed per institutional guidelines.

Red blood cell transfusion and platelet transfusion should be given per institutional guidelines. Erythropoietin-stimulating agent (ESA), Granulocyte Colony Stimulating Factor (G-CSF), and Granulocyte Macrophage Colony Stimulating Factor (GM-CSF) are not permitted.

#### **9.1.5. Reporting of an Overdose**

For NC525, a definitive “overdose” level is unknown at this time. For the purpose of this trial, an overdose of NC525 will be defined as a subject receiving a dose of NC525 in excess of that assigned to them at the time of enrollment unless the alternative dose level was otherwise authorized by the Sponsor prior to administration.

**Any overdose of a study subject with NC525 with or without associated AEs/SAEs, is required to be reported within 24 hours of knowledge of the event to the Sponsor or its designee.** If the overdose results in an AE, the AE must also be recorded on the AE eCRF. Overdose does not automatically make an AE serious, but if the consequences of the overdose are serious, for example death or hospitalization, the event is serious and must be reported as an SAE.

#### **9.1.6. Reporting of AEs**

AEs (including laboratory abnormalities that constitute AEs) should be described using a diagnosis whenever possible rather than by individual underlying signs and symptoms. The investigator, who is a qualified physician, and any designees are responsible for detecting, assessing, documenting, and reporting events that meet the definition of an AE or SAE as well as other reportable safety events. Investigators remain responsible for following up AE, SAEs, and other reportable safety events for outcome.

The severity of AEs will be assessed using NCI CTCAE v5.0 Grades 1 through 5.

If an event is not classified by NCI CTCAE, the severity of the AE will be graded according to [Table 12](#) to estimate the grade of severity.

**Table 12: NCI CTCAE v5.0 Grading Scale**

Grade	Clinical Characteristics
Grade 1	Mild; asymptomatic or mild symptoms; clinical or diagnostic observations only; intervention not indicated.
Grade 2	Moderate; minimal, local, or noninvasive intervention indicated; limiting age-appropriate activities of daily living.

Grade	Clinical Characteristics
Grade 3	Severe or medically significant but not immediately life-threatening; hospitalization or prolongation of hospitalization indicated; disabling; limiting self-care activities of daily living.
Grade 4	Life-threatening consequences: urgent intervention indicated.
Grade 5	Death

The occurrence of AEs should be sought by nondirective questioning of the subject during the screening process after signing the ICF and at each visit during the study. Adverse events may also be detected when they are volunteered by the subject during the screening process or between visits, or through physical examination, laboratory test, or other assessments. To the extent possible, each AE should be evaluated to determine:

- The severity grade (NCI CTCAE v5.0 Grade 1 to 5).
- Relationship to study drug: unrelated, unlikely related, possibly related, probably related, and definitely related. See [Appendix 1](#).
- The start and end dates, unless unresolved at final follow-up.
- The action taken with study drug.
- The event outcome (e.g., not recovered/not resolved, recovered/resolved, recovering/resolving, recovered/resolved with sequelae, fatal, unknown).
- The seriousness, as per SAE definition provided in [Section 9.1.2](#).

All AEs should be treated appropriately. If an AE is treated with a concomitant medication or nondrug therapy (e.g., procedure), this action should be recorded on the AE eCRF and the event should be correlated as the indication on the appropriate eCRFs as applicable.

Once an AE is detected, it should be followed until it has resolved or until it is judged to be permanent; assessment should be made at each visit (or more frequently if necessary) of any changes in severity, the suspected relationship to the study drug, the interventions required to treat the event, and the outcome.

When the severity of an AE changes over time for a reporting period (e.g., between visits), each change in severity will be reported as a separate AE until the event resolves. For example, 2 separate AEs will be reported if a subject has Grade 1 diarrhea, meeting the definition of an AE, that lasts for 3 days before worsening to a Grade 3 severity. The Grade 1 event will be reported as an AE with a start date equal to the day the event met the Grade 1 AE definition and a stop date equal to the day that the event increased in severity from Grade 1 to Grade 3. The Grade 3 event will also be reported as an AE, with the start date equal to the day the event changed in intensity from Grade 1 to Grade 3 and a stop date equal to the day that the event either changed severity again or resolved.

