## **2.2. STUDY ENDPOINTS**

### **2.2.1. Primary Endpoints**

- 1) Safety and tolerability will be assessed by monitoring the frequency, duration, and severity of adverse events (AEs). **Note:** Toxicity grading per NCI CTCAE v5.0
- 2) The recommended Phase 2 dose (RP2D) of NC525 in subjects with advanced myeloid neoplasms.
- 3) The MAD, PAD, and MTD of NC525 will be defined in subjects with advanced myeloid neoplasms.

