### 3.2.2. Dose Levels and Cohorts

The Dose Escalation part of the study will begin the following planned dose levels and cohorts:

- **Dose Level 1:** 2 mg/kg biweekly\*\*
- **Dose Level 2:** 2.5 mg/kg\* weekly\*\*
- **Dose Level 3:** 4.5 mg/kg weekly\*\*
- **Dose Level 4:** 10 mg/kg weekly\*\*
- **Dose Level 5:** 20 mg/kg weekly\*\*
- **Dose Level 6:** 30 mg/kg weekly\*\*

\*\* Cohort 1: Biweekly (Q2W) for Cycles 1 through 6 followed by every 4 weeks (Q4W) thereafter. Cohort 2 and above: Weekly (QW) dosing for Cycles 1 and 2. Subjects may continue QW dosing until overall response (e.g., CR, CRh, or CRi) is achieved, at which time they may switch to Q2W dosing.

The planned dose levels for Dose Escalation include a maximum dose increment of less than a half-log (233%) between each dose level. Using the Escalation/De-escalation Rules governed by the BON design, if criteria is met allowing dose escalation, the subsequent dose level will first be evaluated against the Dose Increment Modification Rules For Dose Escalation ([Table 2](#)) taking into consideration the number of adverse events (Grade  $\geq 2$ ) and dose limiting toxicities which occurred at the current dose level prior to selecting the next dose.

In the event a dose increment modification is indicated during the Dose Escalation phase of the study, an ad-hoc safety meeting will occur with the Clinical Study Team to review the adverse event(s) against the qualifying criteria before any dose modifications are made.

All Adverse Events (excluding AEs unequivocally due to the underlying disease or an extraneous cause) occurring during the DLT Observation Period will be evaluated against the Dose Increment Modification rules, as follows:

- Limit the maximum dose increment to 100% if patients of a given cohort experience one Grade  $\geq 2$  AE (except for AEs unequivocally due to the underlying disease or an extraneous cause) during the DLT period.
  - *Example: If one  $\geq$  Grade 2 AE occurs in Dose Cohort 1 (2mg/kg), the subsequent dose level will be increased by 100% (4mg/kg) instead of the originally planned dose of 4.5mg/kg.*

- Limit the maximum dose increment to 50% if patients of a given cohort experience two or more Grade  $\geq 2$  AEs (except for AEs unequivocally due to the underlying disease or an extraneous cause) during the DLT period.

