#### 10.3.1.1. Adverse Events

A treatment-emergent adverse event (TEAE) is any AE either reported for the first time or worsening of a pre-existing event after the first dose of study drug. Analysis of AEs will be limited to TEAEs, but data listings will include all AEs regardless of their timing to study drug administration. Adverse events will be tabulated by the MedDRA preferred term and system organ class. Severity of AEs will be based on the NCI CTCAE v5.0 using Grades 1 through 5.

The subset of AEs considered by the investigator to have a relationship to study drug will be considered treatment-related AEs (TRAEs). If the investigator does not specify the relationship of the AE to study drug, then the AE will be considered treatment related. The incidence, frequency, duration, and severity of all AEs (regardless of causality) will be tabulated.

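### AE records split at every severity change are tabulated without being rejoined, which raises event counts and shortens durations; the dose-increment rule also leaves its counting unit unstated

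*Combined protocol and SAP*

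**What the plan says.** **Recording.** Section 9.1.6, in the text after Table 12, provides that when an AE changes grade, "each change in severity will be reported as a separate AE until the event resolves". Its example is explicit: "2 separate AEs will be reported if a subject has Grade 1 diarrhea" that lasts three days and then worsens to Grade 3. The Grade 1 record stops on the day the Grade 3 record starts, and the Grade 3 record gets "a stop date equal to the day that the event either changed severity again or resolved".

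**Analysis.** Primary endpoint 1 (Section 2.2.1) is based on the frequency, duration and severity of AEs. Section 10.3.1.1 states: "The incidence, frequency, duration, and severity of all AEs (regardless of causality) will be tabulated". It gives no event identifier, no rule for joining records and no definition of duration across grades. Section 10 leaves further analysis detail to a supplemental SAP.

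**Dose increments.** Section 3.2.2 bases the cap on the next increment on the number of Grade 2 or higher AEs in the cohort. For one: "Limit the maximum dose increment to 100% if patients of a given cohort experience one Grade" 2 or higher AE. For more: "Limit the maximum dose increment to 50% if patients of a given cohort experience two or more Grade" 2 or higher AEs. Neither the text nor Table 2 says whether an AE here is a record, an episode or an affected subject. For DLTs the unit is given: the note to Table 1 counts subjects who had one or more.

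**First dose level.** Step 1 of Section 10.2.1 adds two subjects at dose level 1 if the first subject has a DLT or at least two Grade 2 toxicities. It also states no unit.

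**The concern.** Splitting records by grade is a sound way to capture data, and the grade- and time-based DLT criteria in Table 6 need it. The difficulty comes when the split records become the unit of analysis. A continuing event whose grade moves up and down then looks like several short events, while an equally long event at a constant grade looks like one long event. Event frequency and mean duration would partly measure how often a site re-graded, and both are named in the primary safety endpoint and summarised by dose level.

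The same question of unit reaches dose escalation. If the Section 9.1.6 definition of a separate AE is carried into Section 3.2.2, one event in one subject with two segments at Grade 2 or higher can be read as two such AEs.

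**Working it through.** **Inputs.** Recording rule, dates and example: Section 9.1.6. Tabulation: Section 10.3.1.1. Caps of 100% and 50%, and planned doses of 2, 2.5, 4.5, 10, 20 and 30 mg/kg: Section 3.2.2. DLT criteria: Table 6. The only segment length the plan gives is the 3 days at Grade 1; every other day count below is my assumption.

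**1. The plan's own example.** Grade 1 to Grade 3 is one severity change, so k = 1 and k + 1 = 2 records, as the plan says. If the Grade 3 segment lasts d days, the mean recorded duration is (3 + d)/2 against a true length of 3 + d. That is one half for any d; with d = 4 it is 3.5 against 7 days.

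**2. General form.** The segments abut, so their lengths (stop minus start) add up to the full length T. With k changes there are k + 1 records, and the mean recorded duration is T/(k + 1).

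| Course of one event (days) | Records | Records at Grade ≥2 | Mean recorded duration | Duration as one episode |
|---|---|---|---|---|
| Grade 1 (3), 3 (4) | 2 | 1 | 7/2 = 3.5 | 7 |
| Grade 2 (3), 3 (4) | 2 | 2 | 7/2 = 3.5 | 7 |
| Grade 2 (3), 3 (4), 2 (3) | 3 | 3 | 10/3 = 3.3 | 10 |
| Grade 3 (4), 2 (3), 1 (3) | 3 | 2 | 10/3 = 3.3 | 10 |
| Grade 1 (3), 2 (4), 1 (3) | 3 | 1 | 10/3 = 3.3 | 10 |

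Joined, each row is one AE.

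**3. What does not change.** A subject with the Grade 2-3-2 event is one subject at maximum Grade 3 whether the records are split or joined. Subject-level incidence by preferred term and maximum grade is the same either way.

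**4. The increment rule read literally.** The limit is the smaller of the planned dose and current dose × (1 + cap). The plan's examples reproduce: 2 × 1.5 = 3 mg/kg and 2 × 2 = 4 mg/kg. (Those examples name 4.5 mg/kg as the planned dose after 2 mg/kg, while the current list has 2.5 mg/kg; that is a separate inconsistency to reconcile.) The table shows what one event with two Grade ≥2 segments does if counted once or twice, with no DLT.

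| Planned step (mg/kg) | Planned increment | Limit if counted once (100%) | Limit if counted twice (50%) |
|---|---|---|---|
| 2 to 2.5 | 25% | 2.5 | 2.5 |
| 2.5 to 4.5 | 80% | 4.5 | 3.75 |
| 4.5 to 10 | 122% | 9 | 6.75 |
| 10 to 20 | 100% | 20 | 15 |
| 20 to 30 | 50% | 30 | 30 |

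The unit matters at three of the five steps. These figures show only that the two readings differ; they do not say which is right.

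**5. Overlap with the DLT rule.** Under Table 6 a nonhematologic Grade 3 adverse reaction lasting more than 72 hours is a DLT, fatigue excepted, and so is any nonhematologic Grade 4 reaction. Section 3.2.2 already applies the 50% cap after one DLT. A 4-day Grade 3 segment is 96 hours, so such events would often be capped at 50% however the AEs are counted. The unit decides the cap mainly for Grade 3 segments of 72 hours or less, fatigue, hematologic events that are not DLTs, and events that ease from Grade 2 to Grade 1 and return to Grade 2 without resolving.

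**6. Dose level 1 trigger.** A Grade 2-3-2 event gives two Grade 2 records. If its Grade 3 segment is not a DLT, whether the trigger is met depends on the unit.

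**The case against.** The strongest reply is that Section 9.1.6 is a reporting instruction, not an analysis rule. It refers throughout to one continuing event, and because adjoining records share a date, episodes can be rebuilt from the data as captured. Section 10 summarises categorical data by number and percentage of subjects, and the supplemental SAP, which is not among the documents, may hold a joining rule. This is right about the data and about subject-level incidence. It does not settle the event-level tables: Section 10.3.1.1 names frequency alongside incidence, and names duration, and as written both rest on AE records.

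On escalation, a reader might infer that any worsening event trips the 50% cap and distorts dose finding. The documents do not support that:

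- The cap needs two segments at Grade 2 or higher. The protocol's own Grade 1 to Grade 3 example has one.
- Direction is not the point: an improving Grade 3 to Grade 2 event has two such segments as well.
- Many qualifying events are already DLTs carrying the same cap, and two of the five planned steps are unaffected.
- AEs clearly due to the disease or an outside cause are excluded, and the Clinical Study Team meets to review the events before an increment is changed.
- Double counting can only make an increment smaller.

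What survives is narrower. The team is asked to apply criteria whose counting unit is not stated, so similar cohorts could be handled differently. The documents give no rate of re-grading, so no probability can be attached to this.

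**Conclusion.** The point holds for the analysis. Followed as written, Section 10.3.1.1 counts an event with k severity changes as k + 1 AEs and gives it a mean recorded duration of 1/(k + 1) of its true length. This rests on three conditions: AE records are the unit of the frequency and duration tables, duration is stop minus start, and no joining rule exists in the supplemental SAP. A reader might go further and infer that the incidence figures are wrong too; they are not, because the number of subjects by preferred term and maximum grade is unchanged. It is worth correcting before the tables are programmed, since two of the three attributes in primary endpoint 1 are affected and the correction needs no new data.

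For Section 3.2.2, Table 2 and Section 10.2.1 the finding is an undefined counting unit, not a demonstrated error in dose assignment. Read together with Section 9.1.6, one event with two Grade 2 or higher segments could count twice under the increment rule.

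**What to change.** **Analysis.** Keep the grade-level capture in Section 9.1.6. In Section 10.3.1.1, for the event-frequency and duration tables, join contiguous records of the same preferred term in the same subject (stop date of one equal to start date of the next) into one episode. Give the episode its maximum grade and a duration from first start to last stop. The cost is a linking variable, a programming step and a sentence of text.

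**Escalation text.** Reconcile Section 3.2.2, Table 2, the matching synopsis text and step 1 of Section 10.2.1 with Section 9.1.6, and state whether each counts records, episodes or subjects, as the note to Table 1 does for DLTs. Which unit applies is the sponsor's decision. The cost is a sentence in each place.
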